### C.3.5 Study Drug Discontinuation

Investigators will consider terminating study participation for any subject due to any adverse event(s) (including clinically significant laboratory results) which, in the opinion of the investigator, would compromise the continued safe participation of the subject in the study. Significant non-compliance with the protocol requirements may also necessitate discontinuation. Pregnancy during study participation is an automatic criterion for permanent study drug discontinuation.

### **C.4. Potential Drug Interactions**

CBDV undergoes phase 1 metabolism via CYP2C19. CYP2C8 and CYP3A4 are also capable of CBDV hydroxylation. CBDV was a potent competitive inhibitor of CYP2C19 ( $K_i = 0.586 \mu\text{M}$ ). CBDV was a relatively potent reversible inhibitor of CYP1A2, 2B6 and 2C9 ( $\text{IC}_{50}$  values all  $< 2 \mu\text{M}$ ). CBDV was a relatively weak inhibitor of CYP2D6, 2C8 and 3A4 ( $\text{IC}_{50}$  values between  $10\text{--}30 \mu\text{M}$ ), and did not inhibit CYP2E1. In a further study in HLMs, CBDV was a relatively moderate time-dependent inhibitor of CYP3A4 ( $K_i$  of  $14.7 \mu\text{M}$  and a  $K_{\text{inact}}$  of  $0.063 \text{ min}^{-1}$ ). Careful titration of CBDV in patients taking concomitant medications metabolized by CYP3A4 or CYP2C19 is advised, with plasma monitoring of such medications or their metabolites to be undertaken at the investigator's discretion.

CBDV caused a small but significant increase in CYP2B6 mRNA levels which appeared to be concentration dependent. However, this was only observed at concentrations  $> 10 \mu\text{M}$  ( $2864 \text{ ng/mL}$ ). Hence, CBDV is unlikely to produce any significant effects at clinically relevant doses/concentrations. In vitro, CBDV potently inhibited UGT1A9 ( $\text{IC}_{50} = 0.185 \mu\text{M}$ ) and UGT2B7 ( $\text{IC}_{50} = 0.654 \mu\text{M}$ ) respectively and weakly inhibited enzyme activity mediated by UGT1A1 ( $\text{IC}_{50} = 13.0 \mu\text{M}$ ). Care should be taken when introducing CBDV to existing treatment regimens which contain medications solely or primarily metabolized by UGT1A9 and UGT2B7.

CBDV inhibited P-gp and OCT1 in vitro with  $\text{IC}_{50}$  values of  $20.4 \mu\text{M}$  ( $5843 \text{ ng/mL}$ ) and  $6.77 \mu\text{M}$  ( $1939 \text{ ng/mL}$ ), respectively. The main plasma phase I metabolite of CBDV, 7-COOH-CBDV, inhibited P-gp, BCRP, BSEP, OATP1B1, OATP1B3, OAT1 and OAT3 with  $\text{IC}_{50}$  values  $> 25 \mu\text{M}$  ( $7160 \text{ ng/mL}$ ). There is potential to reach these concentrations in vivo, however, a clinically efficacious dose has yet to be established in humans.

As there has been limited clinical exposure to CBDV to date, the potential incidence of DDIs in humans with CBDV has not been established. In addition, the dose/exposure of CBDV required to establish/maintain efficacy also requires further evaluation. GW Pharmaceuticals advises in the IB that it would be prudent for the investigator to monitor subjects carefully in this regard, particularly if they are taking concomitant medications which undergo phase 1 metabolism via CYP2C19 or CYP3A4 or phase 2 metabolism via UGT1A9 or UGT2B7. This monitoring will be done via routine drug level monitoring as described below.

### **C.5. Safety Assessments**

Full panel of safety labs (CBC with differential, basic metabolic panel and liver function tests) and if participant is taking one or more of the anti-epileptic medications, concomitant plasma drug levels for valproic acid, lamotrigine, oxcarbazepine, phenytoin and clobazam, which are drugs metabolized by phase 1 metabolism via CYP2C19 or CYP3A4 and phase 2 metabolism via UGT1A9 or UGT2B7, will be drawn at baseline, week 4, and week 12. Additional liver function test will be drawn at week 2 to monitor response during dose escalation. Other laboratory studies may be ordered if clinically indicated. Home medications may be monitored on a patient by patient

basis if there are safety concerns suspected to be related to a drug-drug interaction. (See Appendices A and B for the lists of drugs metabolized by phase 1 via CYP2C19 or CYP3A4 and phase 2 metabolisms via UGT1A9 or UGT2B7).

While there is no formal drug-drug interaction data to demonstrate the effect of CYP2C9 inducers and inhibitors on the PK of CBDV, PK data from study GWEP1330 does not indicate an interaction of concern. In Part A of the trial, the PK and safety of CBDV was assessed when given concomitantly with inducer AEDs (including any of the following: Carbamazepine, phenobarbital, primidone or phenytoin) and inhibitor AEDs (Valproic acid). Data indicated there were no notable differences in the safety or PK results obtained for CBDV and its metabolites between the AED groups. From a safety point of view, CYP2C9 is not the sole metabolic pathway for CBDV. CBDV may also be metabolized by other cytochrome p450 enzymes including 2C8 and 3A4. Based on this indicative data we consider the exclusion of medications that are potent inhibitors or inducers of CYP2C9 is not required.

For any clinically significant ( $>3\times$  ULN) elevation of ALT or AST, the following laboratory measures, at minimum, should be assessed within 72 hours: repeat ALT/AST, total bilirubin, alkaline phosphatase, and GGT.

Study drug will be discontinued in subjects who have:

1.  $>10\%$  Weight gain
2. Clinical signs of pancreatitis confirmed with amylase and lipase elevation  $>2\times$  ULN
3. ALT or AST  $>8\times$  ULN
4. ALT or AST  $>5\times$  ULN for more than 2 weeks
5. ALT or AST  $>3\times$  ULN and TBL  $>2\times$  ULN
6. ALT or AST  $>3\times$  ULN with the appearance of fatigue, nausea, vomiting, right upper quadrant pain or tenderness, fever, rash, and/or eosinophilia ( $>5\%$ )

All trial subjects with elevated LFTs will be followed until all abnormalities return to the baseline state as assessed by the investigator with AST/ALT  $< 3\times$  ULN.

- Pregnancy test, if applicable, will be performed at screening, baseline, weeks 2, 4, and 12 via urine or blood
- ECG will be performed at baseline and week 12 or at the time of early termination should this arise.
- Columbia Suicide Severity Rating (C-SSRS) Scale -The Investigator will attempt to administer the Columbia Suicide Severity Rating Scale in the beginning and at each visit. If the C-SSRS cannot be performed then a clinical assessment of suicidality will be done

### **C.6. Concomitant Treatment**

All concomitant conditions will be treated in accordance to prevailing medical practice. Any medications or non-drug therapies used prior and during the study will be recorded. Any changes to existing medications or addition of new medications should be discussed with the investigator. For those requiring these changes, subjects' families will be instructed to discuss these changes with study staff and staff may decide the changes are so substantial as to recommend withdrawal from the study.

### **C.7. Risk Benefit Analysis**

This protocol is considered to involve greater than minimal risk, but it presents the prospect of

direct benefit to the individual subjects (HHS Code of Federal Regulations 45 CFR 46.405). The research is more than minimal risk because of the administration of active medication with known and unknown side effects. Participation in the study directly benefits subjects in close clinical monitoring, and families will receive feedback on the results of the cognitive and behavioral testing, which may be used to help guide educational and support services for the subject.

## **C.8. Definition of Primary and Secondary Outcomes/Endpoints**

### **I. Outcome measures**

Project outcomes will be determined by changes in score of parent and clinician rated measures from baseline to week 12 and comparisons of week 12 measures between active treatment and placebo groups. Assessments will be administered according to the schedule in Table 1. Future studies may incorporate additional long-term maintenance studies to provide more data on safety and efficacy. Additions measures will be completed per Schedule of Events.

### **II. Study Time Commitment and Reduction of Burden:**

Every effort has been made to reduce the time burden on patients and caregivers. As in the case in most clinical trials, the most significant burden to the parent and child are logistics to follow study assessment procedures. To minimize patient burden and facilitate recruitment in this study that involves a rare disorder, the study will utilize remote visits in combination to in person visits. Outcome measures are selected to keep parent questionnaire between 15 to 20 minutes to complete, and child assessments are kept to a minimum. The screening visit will be conducted remotely to reduce burden of travel and minimize burdens to participants who may not meet full participation criteria.

The time commitment and study burden are similar to other studies in this population. If needed, visits can be split into two visits. Caregivers may prefer to attend a visit by themselves without their child to complete their measures. As much flexibility in scheduling as necessary will be given to the patients and families. Reimbursement for time and travel is provided at each visit (\$50 at screening, \$40 all subsequent visits).

## **C.8.1. Primary Outcomes**

### **I. Aberrant Behavior Checklist (ABC) – Irritability Subscale**

The ABC-I is a well-characterized outcome that is accepted by the FDA for the purpose of labeling, and is one of the best and most validated outcome measures in the developmental disabilities. An inclusion cutoff of 18 or higher on the ABC-I at screening was chosen based on multiple medication trials with irritability as the primary target. This includes those that led to the approval of risperidone and aripiprazole for irritability in children with ASD aged 5 to 17. It is completed by caregivers at screening, baseline, weeks 4, 8 and 12, and takes approximately 20 minutes to complete.

The ABC-Irritability subscale consists of 15 questions that address the presence of aggression, tantrums and/or self-injury. The scores on the subscale range from 0 to 45. Subjects must score an 18 or higher at screening to be included in the study.

## **C.8.2. Secondary Outcomes**

### **I. Repetitive Behavior Scale – Revised (RBS-R)**

The RBS-R is a 44-item self-report questionnaire that is used to measure the breadth or repetitive behavior in children, adolescents and adults with ASD. The RBS-R provides a quantitative, continuous measure of the full spectrum of repetitive behaviors. The RBS-R consists of six subscales including: Stereotyped Behavior, Self-injurious Behavior, Compulsive Behavior, Routine Behavior, Sameness Behavior, and Restricted Behavior that have no overlap of item content. The RBS-R is a well-validated and consistent measure of repetitive behaviors in developmental disorders. It has been used in studies with adults, adolescents, and children with success. The scale is completed by the caregivers and takes approximately 20 minutes.

## II. Children's Yale-Brown Obsessive-Compulsive Scale (CY-BOCS)

The CY-BOCS is 10-item clinician measure designed to assess the severity of obsessive-compulsive symptoms in children and adolescents over the previous week. It consists of four primary sections including Obsessions checklist, Severity items for Obsessions, Compulsions checklist and severity items for Compulsions and a set of investigational items. Improvement on this scale was associated with improvements in caregiver quality of life in our 8-week study of intranasal oxytocin.

## III. Hyperphagia Questionnaire for Clinical Trials (HQ-CT)

The HQ-CT is a 9-item caregiver-reported measure of food-seeking behaviors that was used in the phase 3 beloranib trial.

## IV. ActiGraph GT9X-BT activity monitors

Actigraph activity monitors are a well validated activity sleep monitoring device that has been utilized widely in clinical trials and health research, measuring sleep latency, total sleep time, and sleep efficiency.

## V. Clinical Global Impression Scale – Improvement (CGI-I):

The CGI-I will be used as a measure of improvement and contains a 7-point scale as follows: 1 = very much improved, 2 = much improved, 3 = minimally improved, 4 = no change, 5 = minimally worse, 6 = much worse, 7 = very much worse. The CGI-I is a clinician rated global measure of improvement and has been used as a measure in previous clinical psychopharmacology trials that takes 5 minutes to complete.

## VI. Caregiver Strain Questionnaire (CSQ).

The Caregiver Strain questionnaire is a 21-item self-report questionnaire that was developed to assess caregiver strain for families with a child living with an emotional or behavioral disorder. It is completed by the caregivers and takes approximately 15 minutes.

## VII. Montefiore Einstein Rigidity Scale-Revised-PWS (MERS-R-PWS)

The Montefiore-Einstein Rigidity Scale-Revised-PWS (MERS-R-PWS) is designed to assess three domains of rigid behavior in individuals with PWS:

1. Behavioral Rigidity (e.g., Insistence on sameness, things must be done in his/her way, etc.)
2. Cognitive Rigidity (e.g., Special interests, inflexible adherence to rules, etc.)
3. Protest (in response to deviation from rigidity; e.g., tantrum, irritability, arguing)

The MERS-R-PWS is a clinician-rated scale and takes about 20 minutes to complete.

VIII. Aberrant Behavior Checklist (ABC) subscales in lethargy/social withdrawal, stereotypic behavior, hyperactivity/noncompliance, and inappropriate speech

The ABC is an informative rating instrument that was empirically derived by principal component analysis to measure behavior in those with developmental disability and ASD. It contains 58 items that resolve into 5 subscales. The subscales and the respective number of items are as follows: (a) irritability – 15 items, (b) lethargy/social withdrawal – 16 items, (c) stereotypic behavior – 7 items, (d) hyperactivity/noncompliance – 16 items, and (e) inappropriate speech – 4 items. The ABC was designed to be completed by any adult who knows the patient well, such as a parent/caregiver or teacher. This instrument measures behavior on a four-point severity scale where 0 = no problem at all, 1 = behavior is a problem but in a slight degree, 2 = problem is moderately serious, and 3 = problem is severe in degree. The ABC has been used in multiple trials to measure changes in irritability (as seen in our preliminary data) and social withdrawal, with success. It is completed by caregivers and takes approximately 20 minutes.

### **C.8.3. Other Assessments**

#### **I. Clinical Global Impression-Severity (CGI-S)**

The CGI-S reflects the rater's impression of the subject's current illness state on a 7-point scale ranging from no symptoms (1) to very severe (7). Whenever possible, for any individual, these assessments should be done by the same rater throughout the study.

#### **II. IQ Test: Stanford-Binet Intelligence Scales, Fifth Edition-Abbreviated:**

The Stanford-Binet will be administered to obtain data on adaptive behavior and intellectual functioning for correlation during analyses. It is a gold standard measure of intelligence used in clinical and research settings in those aged 2 to 85 years. The fifth edition has a 50/50 balance between verbal and nonverbal subtests, and the Stanford-Binet is considered the best assessment of intelligence in those with intellectual disability and mental retardation. The abbreviated version will be used for this study, which consists of 2 subtests and takes approximately 10-20 minutes to complete (administration time is approximately 5 minutes per subtest).

#### **III. Columbia Suicide Severity Rating (C-SSRS) Scale**

The assessment for suicidality in clinical trials is a requirement for CNS active molecules requested by Health Authorities. The C-SSRS (<http://www.cssrs.columbia.edu>) is a clinician-rated tool recommended by Health Authorities including the FDA to assess previous suicidality of a subject at screening (C-SSRS screening to be used at screening) as well as any new instances of suicidality during the clinical study (C-SSRS since last visit, to be used at subsequent visits). The C-SSRS incorporates a structured interview to prompt recollection of suicidal ideation, including the intensity of the ideation, behavior, and attempts with actual/potential lethality.

Age and capability appropriate versions of the C-SSRS will be used. The young children/cognitively impaired version will be used for children 5 – 11 years old and all cognitively impaired patients regardless of age. For participants that are unable to be directly assessed for suicidality (nonverbal, low functioning) and participants younger than 12, clinician will ask the caregiver the following additional questions:

- (1). Suicidal Ideation: Has the child wished he/she were dead or wished they could go to sleep and not wake up?
- (2). Suicidal Behavior: Has the child made a suicide attempt? Has he or she done anything to harm him or herself?

(3). Self-injurious Behavior: Has the child engaged in non-suicidal self-injurious behavior?

If the Investigator concludes on a suicidality risk of the subject, the Investigator must take care for further evaluation of the risk, which may involve local experts in the field of suicidality.

#### IV. Safety labs

CBC with differential, basic metabolic panel, liver function test, and concomitant plasma drug levels for valproic acid, lamotrigine, oxcarbazepine, phenytoin and clobazam, which are drugs metabolized by phase 1 metabolism via CYP2C19 or CYP3A4 and phase 2 metabolism via UGT1A9 or UGT2B7, will be obtained at baseline, week 4 and week 12. Additional liver function test will be drawn at week 2 to monitor response to dose escalation. Other lab studies maybe ordered if there are clinically indications that requires further investigation. Week 2 and Week 4 labs will be obtained via outpatient Quest lab.

#### V. Pregnancy test

For female participants reached menarche, pregnancy test will be performed at screening, baseline, week 4, and week 12. Pregnancy test (hCG) may be collected either by urine or blood.

#### VI. Drug testing

Drug testing will take place at screening and at baseline for all major drugs of abuse. In the case of positive urine samples, testing will be repeated for confirmation. We will adhere to all institutional/regulatory reporting requirements for any positive test results. Confirmed positive results will lead to exclusion. For patients who are unable to provide urine sample during screening visit, drug screening will be performed at first in person clinic visit via either urine or blood prior to study randomization.

#### VII. Menstrual Diary

Parent and participant will be asked to keep a record of menstruation throughout the study for all female subjects who have reached menarche and are having menstrual period. The diary will be reviewed monthly.

#### VII. Dietary Diary

Dietary intake will be assessed using the National Cancer Institute (NCI) 24-hour automated recall method, which will be completed by the primary caregiver in 15 to 20 minutes. Dietary recalls will be obtained to assess pre-treatment dietary habits at baseline, and assessed at monthly interval during in person visits at weeks 4, 8, and 12. The NCI nutritional program output will allow for secondary analyses of impact of treatment on both dietary macronutrient ratio (percent carbohydrates, proteins and fats) and caloric intake.

#### VIII. Actigraphy

Patient's sleep and activity levels will be assessed using actigraphy. Successfully screened patients will receive the actigraphy device prior to on site visit and will record a minimum of three days of baseline activity data prior to starting study medication. Actigraphy is captured automatically via cloud service and will be reviewed at in clinic visit.

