### **Secondary Aims**

To compare CBDV vs. placebo on changes from baseline to endpoint in:

1. Repetitive behaviors using the Repetitive Behavior Scale – Revised (RBS-R) and the Children's Yale- Brown Obsessive Compulsive Scale (CY-BOCS).
2. Hyperphagia using the Hyperphagia Scale for Clinical Trials (HQ-CT)
3. Sleep quality using ActiGraph GT9X-BT activity monitors.
4. Rigid behaviors using the Montefiore-Einstein Rigidity Scale-Revised-PWS (MERS-R-PWS)
5. Global improvement using the Clinical Global Impressions Scale-Improvement (CGI-I) and Caregiver Strain Questionnaire (CSQ).
6. ABC subscales in lethargy/social withdrawal, stereotypic behavior, hyperactivity/noncompliance, and inappropriate speech

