#### **II. Screening (remote)**

The screening visit will be conducted remotely and occur prior to administration of CBDV to confirm that eligibility and safety criteria are met before study entry.

The screening visit will begin with a member of the study staff going through the Informed Consent with each subject and his/her parents or guardian where they discuss the nature of the study, its requirements, and its restrictions. Subjects age 7 and older will be assessed for capacity and asked to give assent to participate if able to do so.

After obtaining informed consent, the clinician will conduct a medical and psychiatric history

interview, including confirmation of PWS diagnosis using patient medical records and previous genetic testing. The clinician will review patient and parent questionnaires to assess participant eligibility. A score of 18 or higher on the Aberrant Behavior Checklist – Irritability and 4 or more at the Clinical Global Impression Scale Severity (CGI-S) are required per inclusion criteria. Also at screening, the clinician will review concomitant medications with the participants and assess stable pharmacologic, educational, behavioral and/or dietary interventions over past 4 weeks.

If patient is a good study candidate, they will be scheduled and instructed to go to a local Quest lab for drug testing, safety labs including CBC, BMP, LFT, and if applicable, pregnancy test (for female reaching menarche).

After reviewing the lab results, if the subject qualifies for enrollment based on Inclusion and Exclusion criteria, they will be informed and scheduled for an in-person baseline visit. Actigraphy device will be shipped to the selected participants to capture a minimum of 3 days of baseline activity information prior to in person baseline visit.

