**V. Visit 7 (weeks 12 [End of study or Early Termination], in person):**

Participants will be assessed in person at 12, or sooner if patient had early termination. Patient will be assessed for interval changes including review of concomitant medication and monitor for adverse events. Patient will complete a physical/neurological exam. Safety labs including CBC with differential, BMP, LFT, and if applicable, pregnancy test, concomitant plasma drug levels for valproic acid, lamotrigine, oxcarbazepine, phenytoin and clobazam for those patients who take them, will be obtained. Vital signs, weight measurement and BMI calculation will be performed at each visit. The ABC, RBS-R, CY-BOCS, HQ-CT, Caregiver Strain Questionnaire, CGI-I, CGI-S, MERS-R-PWS, and C-SSRS will be administered. A repeat ECG will be done at week 12. Body composition will be assessed using bio-impedance analysis. Dietary diary will be collected. Blood sample will be collected and preserved for biorepository for consented patients. Actigraphy data will be reviewed.

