## C.10. Schedule of Events

Procedure	Time Needed	Completed By			Screening (Remote)	Baseline (On Site)	Wk 2 (Remote)	Wk 4 (Remote)	Wk 6 (Remote)	Wk 8 (Remote)	Wk 10 (Remote)	Wk 12 / Early Term (On Site)	Wk 14 F/U (Remote)
		Parent	Child	Clinician									
Informed Consent	60 min	X	X	X	X	X							
I/E Criteria	10 min	X		X	X	X							
Medical Hx/Demographic	30 min	X		X	X								
Physical/Neuro Exam	20 min		X	X		X						X	
Psychiatric Interview	30 min	X	X	X	X								
IQ test (SB-5, Abbreviated)	20 min	X	X	X		X							
ECG	20 min		X	X		X						X	
Randomization	0 min					X							
Review Concomitant Medications	5 min	X		X	X	X	X	X	X	X	X	X	X
Drug Test	5 min		X		X*	X							
Pregnancy Test (if applicable)	5 min		X		X*	X		X*				X	
Vital signs, Weight, BMI	15 min		X	X		X						X	
CBC with differential and basic metabolic panel	15 min		X		X*	X		X*				X	
Liver Function Enzymes	15 min		X		X*	X	X*	X*				X	
AED drug levels (if applicable)	15 min		X			X		X				X	
Adverse Event Monitoring	10 min	X		X			X	X	X	X	X	X	X
Menstrual Diary Review (if applicable)	5 min	X				X		X		X		X	
Dispense Medication	5 min	X		X		X		X		X			

Scales	ABC-I	15 min	X			X	X		X		X		X	X
	RBS-R	20 min	X				X		X		X		X	
	CSQ	15 min	X				X		X		X		X	
	CY-BOCS	20 min	X		X		X		X		X		X	X
	HQ-CTx	15 min	X		X		X		X		X		X	X
	MERS-R-PWS	15 min	X		X		X		X		X		X	X
	CGI-I	5 min		X	X				X		X		X	X
	CGI-S	5 min		X	X	X	X		X		X		X	X
	C-SSRS	15 min	X	X	X		X	X	X	X	X	X	X	X
	Dietary Diary	15 mins	X				X		X		X		X	
	Actigraphy **	ongoing	X	X	X		X						X	

\*Denotes visit require outpatient Quest visit

\*\*Actigraphy device will be dispensed to participants after successful screening and prior to baseline visit, will collect minimum of 3 days of baseline data prior to randomization. Information collected continuously and reviewed at in person visit

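### Baseline actigraphy may be as short as three days and no week-12 window is defined, which costs precision in the sleep change scores

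*Combined protocol and SAP*

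**What the plan says.** Section A lists "Sleep quality using ActiGraph GT9X-BT activity monitors" as secondary aim 3, to be compared as change from baseline to endpoint. Section C.8.2 IV describes the device as "measuring sleep latency, total sleep time, and sleep efficiency".

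Three places set the baseline recording, each as a floor of three days:

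- C.8.3 VIII: the participant "will record a minimum of three days of baseline activity data prior to starting study medication".
- C.9.2 II (screening): the device is shipped "to capture a minimum of 3 days of baseline activity information prior to in person baseline visit".
- C.10, footnote to the Schedule of Events: the device "will collect minimum of 3 days of baseline data prior to randomization".

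The anchor differs slightly (first dose, baseline visit, randomization). None of the three sets a target length, a number of valid nights, a wear-time rule or a weekday/weekend mix.

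After baseline, the C.10 footnote says: "Information collected continuously and reviewed at in person visit". For week 12, C.9.2 V says only "Actigraphy data will be reviewed". No section says which nights make up the week-12 value or how nights are averaged.

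Section G compares week-12 levels between groups, and also compares change. Change is tested by t-test, or by ANCOVA of the week-12 level if an exploratory check shows that change depends on baseline.

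**The concern.** A mean over three nights carries much of the night-to-night variation in sleep. Which nights they are depends on when the device arrives and when the visit is booked. One participant's baseline could be all weekday nights and another's could be two-thirds weekend. With no defined week-12 window, nothing ensures that baseline and endpoint have a comparable number and mix of nights.

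The two ends differ in one respect. Recording is continuous on treatment, so the endpoint window can still be chosen before unblinding. The baseline cannot be lengthened once drug has started. At stake is the ability of a small trial to see a real effect on sleep latency, total sleep time or sleep efficiency through change from baseline.

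**Working it through.** **1. The plan's own figure.** There is none for sleep. Section H sizes the trial for ABC-I only: SD 8.27, difference 8.26, two-sided 0.05, 80% power.

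n per group = 2 × (1.96 + 0.84)² × (8.27/8.26)² ≈ 2 × 7.85 × 1.002 = 15.7, so 16 per group and 32 in all; 32/0.9 = 35.6, so 36 randomized.

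This reproduces (the exact t-test gives 78.0% power at 16 per group). It matters here only because it fixes the group size. With 16 evaluable per group, 80% power on any continuous outcome needs a standardized difference of about 1.02.

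**2. Weekend content of three nights.** Count Friday and Saturday nights in three consecutive nights, by start day Monday to Sunday: 0, 0, 1, 2, 2, 1, 0. So 3 of 7 start days (43%) give none, 2 of 7 (29%) give one and 2 of 7 (29%) give two. Any 7 consecutive nights hold exactly two.

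Suppose weekend sleep differs by d = 30 minutes (assumed; range 15 to 60). A baseline mean with w weekend nights of three is off the weekly mean by d × (w/3 − 2/7), which is −8.6, +1.4 or +11.4 minutes. The extremes are −4.3 and +5.7 at 15 minutes, and −17.1 and +22.9 at 60. The text counts days, so three calendar days might hold only two full nights.

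**3. Variance of change.** Set single-night variance to 1, with ICC the between-person share. Assumptions not in the protocol: ICC 0.3 to 0.7, true baseline-to-week-12 correlation 0.8, 7-night endpoint. With k baseline nights:

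Var(change) = 2 × ICC × (1 − 0.8) + (1 − ICC)/k + (1 − ICC)/7

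| ICC | k = 3 | k = 7 | Ratio | SD ratio |
|---|---|---|---|---|
| 0.3 | 0.453 | 0.320 | 1.42 | 1.19 |
| 0.5 | 0.438 | 0.343 | 1.28 | 1.13 |
| 0.7 | 0.423 | 0.366 | 1.16 | 1.08 |

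The sample size for equal power rises in the variance ratio, and the detectable difference in the SD ratio.

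**4. ANCOVA residual variance.** Same assumptions.

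Residual = [ICC + (1 − ICC)/7] − (0.8 × ICC)² / [ICC + (1 − ICC)/k]

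| ICC | k = 3 | k = 7 | Ratio |
|---|---|---|---|
| 0.3 | 0.292 | 0.256 | 1.14 |
| 0.5 | 0.331 | 0.291 | 1.14 |
| 0.7 | 0.351 | 0.321 | 1.09 |

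**5. Week-12 level comparison.** Its variance is ICC + (1 − ICC)/7 = 0.400, 0.571 and 0.743. It does not involve k, so the baseline length cannot affect it, but it is larger than the ANCOVA residual in every row.

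**The case against.** The case for leaving the text alone has real substance.

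- **Three days is a minimum.** The device ships before a scheduled visit, so many baselines may be longer. This stands, but then baseline length varies with shipping and scheduling and no rule governs it.
- **Section G has routes that avoid or reduce the cost.** The week-12 level comparison uses no baseline, and ANCOVA shrinks the penalty. A noisy baseline also makes ANCOVA the likely path: under the assumptions above, at ICC 0.3 to 0.5, the correlation of change with a 3-night baseline is about −0.6 to −0.5, which 32 participants would detect at the 5% level about 80% to 95% of the time. This stands, and it means that the sleep objective does not rest wholly on the baseline. ANCOVA nevertheless remains conditional on an exploratory check.
- **The variability figures are assumed.** The protocol supports neither an ICC nor a weekend effect, and one ICC need not suit all three sleep measures. This stands, and it is why a range is shown.
- **Sleep is an unpowered secondary outcome in a pilot described as exploratory.** This stands and limits the weight of the point.

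A reader might infer more than the documents support:

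- *That baseline and endpoint windows are mismatched.* No endpoint window is defined, so the finding is only that matching is not assured.
- *That the arms would be biased.* Baseline nights are recorded before 1:1 randomization, so their weekday mix is unrelated to arm except by chance.
- *That 7 baseline nights would cut error by 40%.* The ratio (2/7)/(1/3 + 1/7) = 0.60 covers only the night-to-night component and needs every night valid. With 5 valid baseline and 7 endpoint nights, the fall is 1 − 0.343/0.476 = 28%; with 5 and 5, it is 1 − 0.400/0.476 = 16%.

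**Conclusion.** The point holds as a minor, inexpensive improvement. The three-day floor permits a noisy baseline of uncontrolled weekday mix, and the undefined week-12 window leaves matching to chance or to a later choice.

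The loss is one of precision. On the stated assumptions, the sample size for equal power in a change-score t-test would be 16% to 42% larger with three baseline nights than with seven. The corresponding figure for ANCOVA is 9% to 14%. If actual baselines run longer than three nights, or some of the seven nights are invalid, the gain is smaller.

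On the same assumptions, prespecifying ANCOVA is worth at least as much as lengthening the baseline. ANCOVA with three nights (0.292, 0.331, 0.351) has a smaller variance than a change-score t-test with seven (0.320, 0.343, 0.366). The two steps together do best.

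**What to change.** - In C.8.3 VIII, C.9.2 II and the C.10 (Table 1) footnote, replace the three-day minimum with 7 consecutive nights before first dose, using the same anchor in all three places.
- Define the sleep endpoint as the last 7 nights before the week-12 visit.
- Apply one valid-night rule to both windows, and weight weekday and weekend nights the same way in each, for example 5:2. A valid-night count alone does not match the mix: five valid nights could be one-fifth weekend at baseline and two-fifths at endpoint. Under 5:2 weights, each window needs at least one valid night of each kind. The weighting costs little: with 4 weekday nights and 1 weekend night, the variance factor is (5/7)²/4 + (2/7)²/1 = 0.209, against 0.200 unweighted.
- In Section G, analyse week-12 sleep by ANCOVA on the baseline value, without the preliminary test of dependence on baseline.

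The cost is about four more days of wear, and a baseline visit booked at least a week after the device arrives. The same device, shipment and visit are used. The endpoint and analysis parts need only text, settled before unblinding; the baseline part helps only participants who have not yet started drug.
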